12.1.4.2. Pharmacokinetic Analyses

Plasma concentrations of SMT C1100 parent and metabolites will be summarised and plotted by time point. Using a model exposure parameters will be predicted for each subject at the relevant visits. These parameters will be used as the exposure parameters when investigating the relationships with other data.

Data will be summarised for each cohort separately, combining Cohorts 1 and 3 (F3 formulation), and over all patients.

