2.0 Study Objectives

2.1 Primary Objectives

The primary objectives for this study are:

- To investigate changes in leg MRI in paediatric patients with DMD, following treatment with SMT C1100 (Cohorts 1 and 2)
- To investigate the relationships between changes in leg MRI with plasma concentrations of SMT C1100 and its metabolites in paediatric patients with DMD, following treatment with SMT C1100 (Cohorts 1 and 2)
- To assess the safety and tolerability of SMT C1100 and its metabolites in paediatric patients with DMD

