5.5 Pharmacokinetics (PK)

Samples will be taken for the determination of SMT C1100, DHDI (SMT022346) and DHDIII (SMT022389) concentrations. The table below details the times when PK samples will be taken:

| Visit | Cohort | | |
|------------------|-------------------------------|-------------------------------|-----------------------------|
| | 1 | 2 | 3 |
| Day 1 | Pre-AM and 3 and 6h post-AM | Pre-AM and 3 and 6h post-AM | Pre-AM and 3 and 6h post-AM |
| Day 7 | | 4h post-AM | 4h post-AM |
| Week 4 | Pre-PM and 4 and 10 h post-PM | Pre-PM and 4 and 10 h post-PM | Pre-AM and 3 and 6h post-AM |
| Week 8 | Pre-AM and 3 and 6h post-AM | Pre-AM and 3 and 6h post-AM | |
| Week 12 | Pre-AM and 3 and 6h post-AM | Pre-AM and 3 and 6h post-AM | Pre-AM and 3 and 6h post-AM |
| Week 24 | Pre-PM and 4 and 10 h post-PM | Pre-PM and 4 and 10 h post-PM | Pre-AM and 3 and 6h post-AM |
| Week 36 | Pre-AM and 3 and 6h post-AM | Pre-AM and 3 and 6h post-AM | Pre-AM and 3 and 6h post-AM |
| Week 48 | Pre-PM and 4 and 10 h post-PM | Pre-PM and 4 and 10 h post-PM | Pre-AM and 3 and 6h post-AM |
| Extension Visits | 4h post-AM | 4h post-AM | 4h post-AM |

These concentrations will be used in a population PK (pop-PK) model through which exposure parameters (C_{max} , $C_{t_{rough}}$, and C_{av}) will be predicted for each subject. The pop-PK model may be reported separately.

Concentrations below the lower limit of quantification (BLQ) will be taken as zero for the calculation of summary statistics for the concentration data.

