9.9 Pharmacokinetic Analyses

Plasma concentrations of SMT C1100, DHDI and DHDIII will be summarized (n, median, minimum and maximum) by cohort, visit and time-point. The summaries will also present the median and the number of subjects who have plasma concentrations below the lower limit of quantification (LLOQ). The SMT C1100 summary will also include the number of subjects achieving SMT C1100 concentrations of ≥ 30 ng/mL and ≥ 70 ng/mL.

The concentration listings will present the data as <LLOQ with the actual limit of quantification value presented.

Individual concentration-time plots will be presented in trellis plots for SMT C1100 and metabolites separately. A log10 scale will be used for the concentration axis. The plots will identify the subject's cohort.

The metabolite ratios (DHDI/SMT C1100 and DHDIII/SMT C1100) will also be plotted over time and will be summarized by cohort, visit and time-point.

Pop-PK analyses are described in a separate Pop-PK analysis plan and may be reported separately.

Observed Week 12 C_{trough} and simulated C_{max} and C_{av} parameters will be summarized. The number of subjects achieving SMT C1100 levels ≥ 30 ng/mL, ≥ 70 ng/mL will also be reported for each parameter.

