9.10 Relationship Analyses (Cohorts 1 and 2)

9.10.1 Relationship with SMT C1100 and Metabolite Exposures

The following Week 12, 24, 36 and 48 data will be plotted against SMT C1100 concentrations:

- MRI parameter changes from baseline (MRS fat fractions for the Vastus Lateralis and Soleus, and MRS T2 for Vastus Lateralis and Soleus)
- %MHCd change from baseline * (Weeks 24 and 48 only)

- Fibre diameter (mean) change from baseline * (Weeks 24 and 48 only)
- Utrophin intensity (mean) change from baseline * (Weeks 24 and 48 only)
- Utrophin heterogeneity score change from baseline * (Weeks 24 and 48 only)
- 6MWD change from baseline
- NSAA (total) change from baseline
- 10 metre walk/run duration change from baseline
- Time to stand change from baseline
- PUL total score change from baseline
- PODCI global function scale change from baseline

* based on average values across samples/sections ([Section 5.3.2](#)).

For a visit, the above response will be plotted separately with relevant observed Week 12 C_{trough} and the simulated parameters C_{max} and C_{av} .

The Pearson correlation coefficients (for each week) will also be presented in the footnote of the plots.

These plots will also be produced for the metabolites DHDI and DHDIII.

Any other exposure response modeling conducted will be reported separately.

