10.0 Changes from Planned Analyses

This analysis plan provides further information to that provided in the study protocol.

Changes from the planned analyses in the protocol include:

- [Protocol Section 12.1.3](#) states that, as the study is open-label, the data will be explored on a regular basis by the sponsor. A data access plan has been written that provides details concerning data accessibility to the study data by company individuals whilst the study is ongoing.
- [Protocol Section 12.1.4.2](#) mentions that PK parameters will be used as the exposure parameters when investigating the relationship with other data. Instead the maximum concentration recorded at the relevant visit will be used in these analyses.
- Cohort 3 efficacy data will not be combined with Cohort 1 and 2 data in any analyses.
- The SAP doesn't currently provide details concerning cardiac MRI parameters or the investigation of the relationship of exposure with changes in pulmonary function parameters and blood biomarkers. This detail will be added in a later version.

Important changes from [Version 1.0](#) of the SAP:

- Inclusion of Week 12 and Week 36 data in plots looking at the relationships between efficacy and pharmacodynamic endpoints and also their relationships with pharmacokinetic endpoints and demographics.
- Inclusion of all safety data for the first interim analysis.

- Exclusion of Dystrophin mutation type from the baseline disease characteristic summary.
- Inclusion of FOR-DMD subject's steroid data in steroid use summaries.
- Adjustment of windows to allow a wider window for Weeks 4 and 8, and to allow all available post baseline biopsy data to be included.
- Imputation method for missing activity scores from the NSAA which is only partially completed.

Important changes from [Version 2.0](#) of the SAP:

- Inclusion of fibre diameter and utrophin expression parameters.
- Functional endpoint data from Cohort 3 will not be combined with data from Cohorts 1 and 2.
- Clarification concerning the CSR when Cohorts 1 and 2 have completed their Week 48 visit.
- Inclusion of NSAA total score plots, sometimes replacing those for the NSAA linearized scores.
- Inclusion of waterfall plots, box and whisker plots and mean change from baseline plots for specified endpoints.
- Inclusion of PK parameters (observed [Week 12 C_{trough}] and simulated [C_{max} and C_{av}])
- Reduction in the number of relationship plots – focusing on most important endpoints.

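### The primary leg MRI exposure objective rests on unadjusted weekly Pearson coefficients; a descriptive slope adjusted for baseline and age is a cheap improvement, and one stale metric sentence in SAP 10.0 needs reconciling

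*SAP*

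**What the plan says.** SAP 2.1 lists as a primary objective: "To investigate the relationships between changes in leg MRI with plasma concentrations of SMT C1100 and its metabolites in paediatric patients with DMD" (Cohorts 1 and 2).

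SAP 9.10.1 plots the Week 12, 24, 36 and 48 changes in the four MRS parameters (fat fraction and T2, vastus lateralis and soleus) against exposure. It adds: "The Pearson correlation coefficients (for each week) will also be presented in the footnote of the plots". The plots are repeated for DHDI and DHDIII. Any further exposure-response modelling is to be reported separately, without a method or a commitment. The mixed model that 9.7.1 borrows from 9.6.1 has visit and subject terms but no exposure term.

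On the exposure metric:

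- Protocol 12.1.4.2: "Using a model exposure parameters will be predicted for each subject at the relevant visits", and these are to be the exposure parameters for the relationship analyses.
- SAP 5.5: "These concentrations will be used in a population PK (pop-PK) model through which exposure parameters" (Cmax, Ctrough and Cav) are predicted for each subject.
- SAP 9.9: "Observed Week 12 C_{trough} and simulated C_{max} and C_{av} parameters will be summarized".
- SAP 9.10.1: "For a visit, the above response will be plotted separately with relevant observed Week 12" Ctrough and with the simulated Cmax and Cav.
- SAP 10.0, on departures from the protocol: "Instead the maximum concentration recorded at the relevant visit will be used in these analyses".
- SAP 10.0, on changes since Version 2.0: "Inclusion of PK parameters (observed [Week 12" Ctrough, with simulated Cmax and Cav).

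**The concern.** The study has no control group, so the relation of MRI change to exposure carries much of the weight in judging activity. Cohort 1 takes F3 and Cohort 2 takes F6. Protocol 8.2 reports a more than six-fold higher maximum parent level with F6 at the Cohort 2 dose than with F3. Much of the spread in exposure may therefore lie between two groups that were not randomised. Cohort 2 is enrolled in the US only, Cohort 1 in the UK and US. SAP 3.1 says that balance on age and fat fraction is attempted but not enforced.

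If the two groups also differ in age or baseline fat fraction, that difference enters the Pearson coefficient and can raise or lower it. SAP 9.5 (baseline tables and correlations) and 9.7.1 (MRS change against age and against baseline) would let a reader see the imbalance. Neither gives an exposure estimate with it removed. The PK plots in 9.9 identify cohort; 9.10.1 does not ask for this.

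Separately, the metric sentence in SAP 10.0 is current text and disagrees with 9.9 and 9.10.1 on how exposure is measured for a primary objective.

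**Working it through.** The plan gives no power calculation or expected coefficient, so there is no figure to reproduce. What follows is an illustration.

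**Inputs from the documents**
- n = 30 + 10 (SAP 3.1), taken as complete data.
- Ratio of exposures: six (Protocol 8.2, maximum parent level only).
- Within-cohort geometric CV: 78% to 248% (Protocol 1.1.3). This comes from the F2 study with four boys per group and is borrowed here as a range.

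**Assumptions**
- Log-normal exposure.
- A cohort difference in MRI change of 0.5 or 1 within-cohort SD. No document gives one.

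**Step 1: share of exposure variance between cohorts**
- Within-cohort log variance = ln(1 + CV²): ln(1 + 0.78²) = 0.475; ln(1 + 2.48²) = 1.967.
- Between-cohort log variance = 0.25 × 0.75 × (ln 6)² = 0.602.
- Between-cohort share: 0.602/(0.602 + 0.475) = 56%; 0.602/(0.602 + 1.967) = 23%.

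**Step 2: shift in the raw Pearson coefficient (simulation, 6,000 trials per setting, no drug effect)**

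| Exposure gap | 0.5 SD: CV 78% / 248% | 1 SD: CV 78% / 248% |
|---|---|---|
| Six-fold | 0.15 / 0.09 | 0.29 / 0.17 |
| Three-fold (assumed) | 0.13 / 0.06 | 0.23 / 0.12 |
| Two-fold (assumed) | 0.09 / 0.03 | 0.17 / 0.07 |

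Given cohort, the mean coefficient is within 0.01 of zero throughout. The smaller gaps are shown because the six-fold figure need not hold for trough, average or metabolite levels.

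**Step 3: with a true relation**
Take a true log-scale r of −0.40 and a six-fold gap. The mean raw r is −0.34 / −0.28 (CV 78% / 248%) with no cohort difference. It is about −0.21 with an opposing 0.5 SD difference, and −0.45 / −0.35 with one in the same direction. The relation is weakened or exaggerated, not reversed.

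**Step 4: chance error of one coefficient**
The 95% limit around zero is tanh(1.96/√37) = 0.31 at n = 40.

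**Step 5: how large an age gap is needed**
Assume age is uniform over 5 to 10 years (SD = √(25/12) = 1.44) and explains 20% to 50% of MRI change. The effect per year is √0.2/1.44 = 0.31 SD to √0.5/1.44 = 0.49 SD. A 0.5 SD difference then needs a mean age gap of 1.6 to 1.0 years, and 1 SD needs 3.2 to 2.0 years.

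**Step 6: does the proposed adjustment work?**
When an age gap of the Step 5 size produces the 0.5 SD difference, the unadjusted mean r is again 0.09 to 0.15. Adjusting for age alone brings it to within 0.01 of zero, and no cohort term is needed.

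**Step 7: cost of adding cohort**
The standard error of the log-exposure slope rises by √((between + within)/within) = √(1.077/0.475) = 1.51 at CV 78%, and √(2.569/1.967) = 1.14 at CV 248%.

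**The case against.** The strongest reply is that the study sets out to investigate relationships, is not powered, and has no test or decision rule on these coefficients. The plots are the main output and r is a footnote. This stands, and it limits the grade.

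Pooling is also deliberate: the protocol's rationale wants both formulations so as to cover a wide concentration range. A reader might infer that pooling is itself the fault, or that cohort must always be adjusted for. The documents do not support that. Adjusting for cohort discards the contrast the protocol seeks: in the Step 3 setting at CV 78%, the log-scale partial r given cohort is about −0.28 even without any imbalance.

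The bias figures rest on an assumed cohort difference. If ages differed only by chance, the SE of the mean age gap would be 1.44 × √(1/30 + 1/10) = 0.53 years. A gap of 1.0 to 1.6 years would then arise in about 5% to 0.2% of studies. Allocation is not random, so a systematic gap is possible, but nothing shows one, and balance is actively sought.

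On the metric, 9.9 and 9.10.1 agree with each other, and 10.0 itself records the addition of the PK parameters after Version 2.0. The conflicting sentence is evidently a leftover. A reader might infer that the exposure metric is unsettled; the operative sections do not bear that out. Nor is the observed Week 12 trough an error. Sampling is around the AM dose at Weeks 12 and 36 and around the PM dose at Weeks 24 and 48, and earlier studies showed diurnal variation, so one common pre-AM value is a defensible choice. The visit for the simulated values may be given in the separate Pop-PK plan, which is not among the documents.

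Finally, further modelling may be reported elsewhere, and Protocol 12.1.4 promises summaries by baseline and concentration subgroup. The SAP neither specifies that modelling nor repeats those summaries, so the gap within this SAP remains.

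**Conclusion.** The point holds in a limited form. Within this SAP the leg MRI exposure objective has no estimate beyond an unadjusted weekly coefficient, although baseline MRS value and age are already collected and would remove an imbalance in either. For an assumed 0.5 SD cohort difference the mean shift is about 0.09 to 0.15 with a six-fold gap, and less with smaller gaps. That is under the ±0.31 chance error of one coefficient. The 1 SD case (0.17 to 0.29) is an upper case if age alone is the cause.

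A reader might infer that the planned analysis will produce a false exposure-response signal or hide a real one. The documents do not support that: no cohort difference is shown, the exposure CV is borrowed from another formulation, and the six-fold figure covers maximum parent level only.

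The SAP 10.0 sentence is a real but editorial contradiction. Grade: minor to should-fix.

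**What to change.** 1. For the four primary MRS parameters, add to SAP 9.10.1 a descriptive regression of change from baseline on exposure, adjusted for baseline MRS value and age on Day 1, with slope and 95% CI and no pass/fail rule.
2. Use the model-predicted exposure for the relevant visit, in line with Protocol 12.1.4.2. Protocol 4.2.2 foresees boys permanently off drug who are still scanned, and SAP 5.1 keeps their data with only optional exclusion summaries. A visit-specific prediction can reflect dosing that changed or stopped before the scan; a fixed Week 12 value cannot.
3. Show the same regression with cohort added, as a sensitivity estimate. State that it drops the between-formulation contrast and makes the standard error about 14% to 51% larger (CV 248% to 78%, six-fold gap).
4. Mark cohort on the 9.10.1 plots and keep the Pearson coefficients as descriptive output.
5. Delete the maximum-concentration sentence in SAP 10.0, or reconcile it with 9.9 and 9.10.1.

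The cost is SAP wording and modest programming. No new data are needed: baseline values, age and cohort are collected, and predicted exposures are already planned. The adjustment uses two degrees of freedom, or three with cohort.

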9.10.2 Relationship with MRS parameters

The following Week 12, 24, 36 and 48 data will also be plotted against the MRS parameter changes from baseline (MRS fat fractions and T2s for the Vastus Lateralis and Soleus) for Weeks 12, 24, 36 and 48:

- %MHCd change from baseline * (Weeks 24 and 48 only)
- Fibre diameter (mean) change from baseline * (Weeks 24 and 48 only)
- Utrophin intensity (mean) change from baseline * (Weeks 24 and 48 only)
- Utrophin heterogeneity score change from baseline * (Weeks 24 and 48 only)
- 6MWD change from baseline
- NSAA (total) change from baseline
- 10 metre walk/run duration change from baseline
- Time to stand change from baseline
- PUL total score change from baseline
- PODCI global function scale change from baseline

* based on average values across samples/sections ([Section 5.3.2](#)).

Week 12, 24, 36 and 48 data will be identifiable using different symbols.

The Pearson correlation coefficients (for each week) will also be presented in the footnote of the plots.

9.10.3 Relationship with Biopsy Parameters

The following Week 24 and 48 data will also be plotted against the %MHCd, Fibre diameter (mean), Utrophin intensity (mean), Utrophin heterogeneity score, (changes from baseline (based on average values across samples/sections [Section 5.3.2](#))):

- 6MWD change from baseline
- NSAA (total) change from baseline
- 10 metre walk/run duration change from baseline

- Time to stand change from baseline
- PUL total score change from baseline
- PODCI global function scale change from baseline

Week 24 and Week 48 data will be identifiable using different symbols.

The Pearson correlation coefficients (for each week) will also be presented in the footnote of the plots.

9.10.4 Relationship with Functional Measures of Activity

The following Week 12, 24, 36 and 48 data will also be plotted against each other:

- 6MWD change from baseline
- NSAA (total) change from baseline
- 10 metre walk/run duration change from baseline
- Time to stand change from baseline
- PUL total score change from baseline
- PODCI global function scale change from baseline

Week 12, 24, 36 and 48 data will be identifiable using different symbols.

The Pearson correlation coefficients (for each week) will also be presented in the footnote of the plots.

10.0 Changes from Planned Analyses

This analysis plan provides further information to that provided in the study protocol.

Changes from the planned analyses in the protocol include:

- [Protocol Section 12.1.3](#) states that, as the study is open-label, the data will be explored on a regular basis by the sponsor. A data access plan has been written that provides details concerning data accessibility to the study data by company individuals whilst the study is ongoing.
- [Protocol Section 12.1.4.2](#) mentions that PK parameters will be used as the exposure parameters when investigating the relationship with other data. Instead the maximum concentration recorded at the relevant visit will be used in these analyses.
- Cohort 3 efficacy data will not be combined with Cohort 1 and 2 data in any analyses.
- The SAP doesn't currently provide details concerning cardiac MRI parameters or the investigation of the relationship of exposure with changes in pulmonary function parameters and blood biomarkers. This detail will be added in a later version.

Important changes from [Version 1.0](#) of the SAP:

- Inclusion of Week 12 and Week 36 data in plots looking at the relationships between efficacy and pharmacodynamic endpoints and also their relationships with pharmacokinetic endpoints and demographics.
- Inclusion of all safety data for the first interim analysis.

- Exclusion of Dystrophin mutation type from the baseline disease characteristic summary.
- Inclusion of FOR-DMD subject's steroid data in steroid use summaries.
- Adjustment of windows to allow a wider window for Weeks 4 and 8, and to allow all available post baseline biopsy data to be included.
- Imputation method for missing activity scores from the NSAA which is only partially completed.

Important changes from [Version 2.0](#) of the SAP:

- Inclusion of fibre diameter and utrophin expression parameters.
- Functional endpoint data from Cohort 3 will not be combined with data from Cohorts 1 and 2.
- Clarification concerning the CSR when Cohorts 1 and 2 have completed their Week 48 visit.
- Inclusion of NSAA total score plots, sometimes replacing those for the NSAA linearized scores.
- Inclusion of waterfall plots, box and whisker plots and mean change from baseline plots for specified endpoints.
- Inclusion of PK parameters (observed [Week 12 C_{trough}] and simulated [C_{max} and C_{av}])
- Reduction in the number of relationship plots – focusing on most important endpoints.
- Clarification concerning the reporting of blood biomarker data.

11.0 Validation

The programming (including quality control) of the analysis datasets and TFLs will be conducted under PRA's standard processes PRS 050 and documented accordingly. The entire set of TFLs will be checked for completeness and consistency prior to its delivery to the client by the lead statistician and a senior level statistician, or above, who is not a member of the project team.

The PRA validation process will be repeated any time the TFLs are redelivered using different data. Execution of this validation process will be documented through the study Table of Programs.

Appendix 1 Glossary of Abbreviations

| Glossary of Abbreviations: | |
|----------------------------|--|
| 6MWD | six-minute walk distance |
| AE | adverse event |
| ALT | alanine aminotransferase |
| AST | aspartate aminotransferase |
| ATC | Anatomic Therapeutic Classification |
| AUC | area under the curve |
| BMI | body mass index |
| BP | blood pressure |
| C4 | 7 α -hydroxy-4-cholesten-3-one |
| CRF | case report form |
| CTMS | Clinical Trials Management System |
| DMC | Data Monitoring Committee |
| DMD | duchenne muscular dystrophy |
| ECHO | echocardiogram |
| ECG | electrocardiogram |
| FEV₁ | forced expiratory volume in 1 second |
| FGF19 | fibroblast growth factor 19 |
| FS | fractional shortening |
| FVC | forced vital capacity |
| GLDH | glutamate dehydrogenase |
| IMP | investigational medicinal product |
| ITT | Intention-to-Treat |
| LLOQ | lower limit of quantification |
| LVEF | left ventricular ejection fraction |
| MEP | maximum expiratory pressure |
| MedDRA | Medical Dictionary for Regulatory Activities |
| MHCd | developmental heavy chain myosin |
| MIP | maximum inspiratory pressure |
| MRI | magnetic resonance imaging |
| MRS | magnetic resonance spectroscopy |
| NSAA | North Star Ambulatory Assessment |

| | |
|--------------|--|
| PCF | peak cough flow |
| PEF | peak expiratory flow |
| PK | pharmacokinetic |
| PODCI | Paediatric Outcomes Data Collection Instrument |
| PT | preferred term |
| PUL | Performance of Upper Limbs |
| QTcB | QT interval, heart rate corrected using Bazett's formula |
| QTcF | QT interval, heart rate corrected using Fridericia's formula |
| SI | international system of units |
| SNIP | sniff nasal inspiratory pressure |
| SOC | system organ class |
| TEAE | treatment-emergent adverse event |
| TFLs | tables, figures and listings |
| ULN | upper limit of normal |

